3.3.7 Other Clinically Significant (determined by PI or AI) Non-Hematological Toxicity

These are adverse events that are felt to be at least possibly related to flavopiridol administration and in the opinion of the PI or AI do not have serious medical consequences (i.e. replaced easily) such as low phosphorus, low albumin or low calcium.

Symptom grade	Management
≤ grade 2	Treat symptomatically
≥ grade 3	Hold next dose until grade 1 or baseline and resume flavopiridol if further therapy is indicated

3.4 STUDY CALENDAR

Studies	Pre-therapy^A	Day -1 or day 1 of each cycle	Weekly during therapy	Every second cycle	Follow-up^B
Hx; PE; VS; PS	x	x			x
Tumor Measurement	x			x	x
CBC/diff	x ^F	x	x		x
Electrolytes, Creatinine/BUN ALT, AST, Bilirubin, LDH, Ca ⁺⁺ , Phos, Mg	x ^F	x	x		x
10 mL red top for serum storage	x	x			x
Clinical PET scan ^D	x				
CT chest/abdomen/pelvis ^C	x			x	x
Bone marrow biopsy & aspirate and peripheral blood for flow cytometry where indicated ^E	x			x ^E	
Tumor biopsy, timed blood collections and/or apheresis ^G	x				
Tumor Lysis Syndrome monitoring		x ^H			

- A- Initial assessment may be performed within 4 weeks prior to starting treatment.
- B- Follow-up to occur every 3-4 months until disease progression requiring initiation of non-protocol therapy.
- C- Extent of CT scans may be limited to assess sites of prior disease.
- D- PET scans will be performed pre-therapy if clinically indicated. PET may be obtained at the first post-treatment restaging in patients in CR.
- E- Obtain pre-treatment and after patients achieve CR by other staging.

F- These laboratory tests must be obtained within one week of initial treatment.

G- Where possible, tumor biopsies will be obtained by core needle biopsy or surgery pre-treatment. In select patients a repeat core biopsy of superficial nodes may be carried out within 24 hours from the end of the first flavopiridol infusion. Snap freeze and store tissue biopsies for translational studies at -80°C. Lymphapheresis may be performed pre-treatment in patients with leukemic MCL and may be repeated after the completion of the flavopiridol infusion. Timed blood samples of 20-40 mL each, typically pre-treatment, at 1 hour, 3hours, 6hours and 24hours may be obtained in selected patients during the first flavopiridol infusion. In patients with leukemic disease this may be repeated during the second flavopiridol infusion. Research blood collections will be limited to less than 450 mL in any 6 week period.

H- Please refer to section 4.3.6 on TLS monitoring for details of what is required.

- **Pharmacokinetics:** Collect one 6 mL sodium heparin tube at the following time points on dose 1 and 2 of cycle 1 only: 30 minutes after the start of the bolus infusion, 4.5 hours and 6 hours after the start of the bolus infusion. All PKs should be placed directly on ice and then refrigerated until specimen is picked up.
- **Microarray analysis:** The pretreatment lymph node biopsy, apheresis or blood sample (in the case of leukemic disease) will be used to perform all standard diagnostic tests. In addition we will extract RNA and protein for research studies. The second apheresis or the timed blood samples following the first treatment of flavopiridol will be used for research studies only. Timed blood samples may be subjected to microarray analysis to assess the effects of flavopiridol on the gene expression in normal and malignant cells.
- **Proteomic analysis:** In protein extracts of tumor cells pre and during therapy we aim to determine activity of key regulatory proteins such as components of the NF-kappa B signal transduction pathway, the levels of cell cycle inhibitors such as p21^{cip} and p27^{Kip-1} and the p53 stress response. Where possible we may initiate studies that aim at characterizing changes in protein levels on a global scale.
- **Tissue immunohistochemistry:** Tumor tissue will be analyzed by immunohistochemistry and may include among other antigens, bcl-2, p53, MUM-1, bcl-6, MIB-1, and CD-10. Antibodies for assessment of cdk2 and cdk4 inhibition will include as many of the following as possible: anti-total Rb, anti-Rb [pT356], anti-Rb [pS249/T252], anti-Rb [pS807/811], anti-Rb [pS780], anti-Rb [pS795], anti-total p27^{Kip1}, and anti-p27^{Kip1} [pT187]. Samples will also be analyzed for expression of cdk2, cdk4 and p16^{INK4A}, Ki67 and TUNEL staining. Assessment of cdk9 inhibition will be performed with anti-cyclin D1 and anti-Mcl-1, as well as anti-total RNA polymerase II, anti-RNA polymerase II [pSer²] and anti-RNA polymerase II [pSer⁵], (if RNA polymerase II antibodies can be optimized for immunohistochemistry).
- Tumor tissue may be stored for future research assays which are related to this study and do not pose an increase in patient risk.
- **Serum storage:** Collect one 10 mL red top tube for serum storage pre treatment and prior to each cycle.

Biopsy Procedure:

Standard techniques will be used for pre-treatment percutaneous biopsies which may include CT and / or ultrasound guided biopsy. In some cases, such biopsies may be expedited and facilitated with the use of navigation tools such as an automated laser angle selector connected to CT scan, or a standard needle guide connected to a protractor to determine which exact angle the biopsy needle will be inserted.

These guiding techniques may occur as maneuvers to facilitate the biopsy, which will take place in the usual conventional fashion, with standard, disposable, conventional spring-loaded biopsy

equipment. Such guiding techniques may add to the reliability of tissue acquisition from specific spatial coordinates of a tumor target. Accurate spatial tissue acquisition may lead to more reliable, accurate and precise tissue characterization, which in turn should be more reproducible. When performing sequential biopsies, the knowledge of sampling location within a tumor may actually help avoid multiple needle punctures or repeat procedures, as might occur when samples are obtained from necrotic regions or regions without high quality mRNA (cDNA) for microarrays or sufficient protein for proteomics analysis.

Sequential biopsy has been used routinely at the NCI as a research and prognostic tool, as well as pathway to surrogate biological markers for tumor response, prognosis, or susceptibility to specific targeted agents. Sequential biopsies are usually performed under the assumption that all tumor is created equal (mRNA and proteins) at a given time point, which is clearly an oversimplification with broad ramifications. Precision biopsy techniques might normalize some of the spatial heterogeneity inherent to tumors. Such normalization (as occurs when repeat biopsies are taken from precisely the same location of tumors) could minimize the added noise from the interpretation of already voluminous and noisy data (as in the case of the gene microarrays).

From the CT-guided biopsy, patients will receive (from two CT scans) a total of 8.0 rem to their kidneys and 5.2 rem each to their stomach, gallbladder wall and lower large intestine. All other organs will receive smaller amounts of radiation. Although each organ will receive a different dose, the amount of radiation exposure patients will receive from these procedures is equal to a uniform whole-body exposure of 1.2 rem. This calculated value is known as the “effective dose” and is used to relate the dose received by each organ to a single value. The amount of radiation received in this study is within the dose guideline established by the NIH Radiation Safety Committee for research subjects. The guideline is for an effective dose not to exceed 5 rem received per year in adults. The NIH Radiation Safety Committee has reviewed the use of radiation in adults in this research study and has approved this use as involving acceptable risk and necessary to obtain the research information desired.

In patients with leukemic disease, apheresis (lymphapheresis) will be performed for research purposes only in lieu of a tissue biopsy.

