2.2 RESEARCH ELIGIBILITY EVALUATION

Blood tests (except serologies) and pregnancy test to be done within one week of study entry, other studies to be done within 4 weeks before study entry:

- Complete History and Physical examination.
- CBC, differential, PT, PTT, SGOT, SGPT, LDH, alkaline phosphatase, bilirubin, albumin, calcium, phosphate, uric acid, creatinine (24 hour creatinine clearance if serum creatinine > 1.5 mg/dL), electrolytes, urinalysis, HIV serology, hepatitis B surface antigen and Anti Hepatitis B core antibody.
- Unilateral bone marrow aspirate and biopsy if not performed within 1 month.
- HCG (urine) in women of childbearing potential.
- Electrocardiogram.
- Staging: CT scans of chest, abdomen and pelvis.
- PET as clinically indicated.
- Head CT or Brain MRI and lumbar puncture with flow and cytology as clinically indicated.

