3.2 DRUG ADMINISTRATION

3.2.1 Phase 1 Dosing and Schedule

The Phase I dose escalation will follow one of two different escalation rates shown in Tables 1 and 2 below. If DLT is observed in 0/3 or 1/6 patients on dose level 1, subsequent patients will be enrolled according to the paradigm described in Table 1 below. If DLT is observed in 2/6 patients on dose level 1, subsequent patients will be enrolled according to the paradigm described in Table 2 below.

Flavopiridol dose levels

Table 1	Cycle 1, Week 1		Cycle 1, Weeks 2–4, AND All weeks During All Subsequent Cycles	
Dose level	Bolus x30 minutes IV	Continuous infusion x 4 hrs	Bolus x30 minutes IV	Continuous infusion x 4 hrs
1	30mg/m ²	30mg/m ²	30mg/m ²	50mg/m ²
2	30mg/m ²	50mg/m ²	30mg/m ²	50mg/m ²
3	30mg/m ²	50mg/m ²	40mg/m ²	60mg/m ²
4	40mg/m ²	60mg/m ²	40mg/m ²	60mg/m ²

Table 2	Cycle 1, Week 1	Cycle 1, Weeks 2–4, AND All weeks During All Subsequent Cycles

Dose level	Bolus x30 minutes IV	Continuous infusion x 4 hrs	Bolus x30 minutes IV	Continuous infusion x 4 hrs
1	30mg/m ²	30mg/m ²	30mg/m ²	50mg/m ²
1A	25mg/m ²	25mg/m ²	30mg/m ²	50mg/m ²
1B	25mg/m ²	25mg/m ²	40mg/m ²	60mg/m ²

- Administer weekly x 4 consecutive weeks, followed by 2 weeks without flavopiridol treatment for a cycle duration of 6 weeks (1 cycle).
- For cycles 2-6, administer the doses given during cycle 1, weeks 2-4 for all doses.
- Administer up to 6 cycles if no disease progression.
- Restage all positive sites of disease after every 2 cycles, except bone marrow which should be repeated after other sites have achieved a CR.
- Administer flavopiridol in the inpatient unit on cycle 1, dose 1 (bolus and infusion).
- Unless medically contraindicated, all patients will receive allopurinol 300 mg per day on cycle 1 x 5 days. All patients should receive at least 200 mL/hr 0.9% Sodium Chloride Injection for 6 hours prior to the first flavopiridol dose. Detailed required guidelines for Tumor Lysis Syndrome prevention is shown in section 4.3.
- If cycle 1, dose 1 is tolerated without TLS, subsequent doses may be administered outpatient.

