3.2.2 Phase 2 Dosing

- Dose will be the MTD from the phase I portion.
- Administer weekly x 4 consecutive weeks, followed by 2 weeks without flavopiridol treatment for a cycle duration of 6 weeks (1 cycle).
- For all weeks of all cycles after cycle 1, patients will receive the dose administered on cycle 1, weeks 2-4.
- Administer up to 6 cycles if no disease progression.
- Restage all positive sites of disease after every 2 cycles, except bone marrow which should be repeated after other sites have achieved a CR.

3.2.3 Definition of Dose Limiting Toxicity:

Dose-limiting toxicity will be determined during the first cycle of treatment and is defined as:

- any grade 3 or greater non-hematologic toxicity excluding transient liver function abnormalities that resolve spontaneously within 10 days and/or transient electrolyte abnormalities that are not life-threatening, or fatigue
- grade 4 thrombocytopenia (< 25,000/mcL) persisting for 4 or more days

- grade 4 neutropenia ANC < 500/mcL persisting for 7 or more days despite the institution of G-CSF
- inability to continue with cycle 2 by 3 weeks after the end of cycle 1. Exceptions to this (i.e. accidents, family emergencies, etc) will be evaluated on a case-by-case basis.
- irreversible \geq grade 2 non-hematologic toxicity
- irreversible grade 3 thrombocytopenia at least possibly due to flavopiridol.
- And is a drug related event with an attribution of possible, probable or definite.

Patients with compromised bone marrow function from lymphoma will not be evaluable for hematologic related DLT. Irreversible is defined as lasting > 3 weeks. All toxicity will be evaluated and scored using NCI Common Terminology Criteria for Adverse Events (CTCAE) version 3.0 until December 31, 2010. CTCAE version 4.0 will be utilized beginning January 1, 2011.

3.3 TREATMENT MODIFICATIONS:

Patients should have recovered toxicities that are clinically significant and attributable to flavopiridol to grade 1 or baseline before beginning another cycle. If toxicity has not resolved to this level within 3 weeks from the end of the previous cycle, flavopiridol will be discontinued.

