5.3 RESPONSE CRITERIA

Response criteria for lymphomas as per Cheson criteria. [18] with modifications as described below. Responses must last for at least 4 weeks off treatment.

- Complete response (CR): Complete disappearance of all detectable clinical and radiographic evidence of disease and disappearance of all disease-related symptoms if present before therapy, and normalization of those biochemical abnormalities (e.g. LDH) definitely assignable to the lymphoma. All lymph nodes must have regressed to normal size (≤ 1.5 cm in greatest diameter if > 1.5 cm before therapy). Previously involved nodes that were 1.1 to 1.5 cm in greatest diameter must have decreased to ≤ 1 cm or by more than 75% in the sum of the products of the greatest diameters (SPD). Spleen, if considered to be enlarged before therapy, must have regressed in size and not be palpable on physical examination. The bone marrow must show no evidence of disease by

histology. Flow cytometric, molecular or cytogenetic studies will not be used to determine response.

- Complete response unconfirmed (CRu): As per CR criteria except that if a residual node is > 1.5 cm, it must have regressed by $> 75\%$ in SPD. Lymphocyte aggregates within the bone marrow must be negative for B-cell markers (e.g. L26).
- Partial response: $\geq 50\%$ decreased in SPD of 6 largest dominant nodes or nodal masses. No increase in size of nodes, liver or spleen and no new sites of disease. Splenic and hepatic nodules must regress by $\geq 50\%$ in the SPD. Bone marrow is irrelevant for determination of a PR.
- Definition of progressive disease (PD): Defined by at least one of the following: $\geq 25\%$ increase in the sum of the products of at least two lymph nodes, appearance of new lymph nodes, $\geq 50\%$ increase in the size of the liver and/or spleen as determined by measurement below the respective costal margin, appearance of new palpable hepatomegaly or splenomegaly that was not previously present, $\geq 50\%$ increase in the absolute number of circulating lymphocytes.
- Definition of stable disease: (SD) will be characterized by not meeting any of the criteria outlined above.

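### Restaging CT may be limited to sites of prior disease, yet PR requires no new sites and new nodes count as PD, so the primary response rate can be overstated

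*Combined protocol and SAP*

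**What the plan says.** Baseline imaging covers the full field. Section 2.2 lists "Staging: CT scans of chest, abdomen and pelvis".

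For restaging, the Study Calendar (3.4) has a row for CT of chest, abdomen and pelvis before therapy, at every second cycle and at follow-up. Footnote C is attached to the whole row: "Extent of CT scans may be limited to assess sites of prior disease". The dosing sections point the same way. Section 3.2.1 has "Restage all positive sites of disease after every 2 cycles", and 3.2.2 repeats it for Phase 2: "Restage all positive sites of disease after every 2 cycles, except bone marrow which should be repeated after other sites have achieved a CR".

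Section 5.3 defines the outcomes more broadly:
- PR: "No increase in size of nodes, liver or spleen and no new sites of disease".
- PD: several criteria, any one of which is enough, among them "appearance of new lymph nodes".
- CR: "Complete disappearance of all detectable clinical and radiographic evidence of disease". New sites are not named here; their absence follows from the word all.

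On PET after treatment, calendar footnote D says only: "PET may be obtained at the first post-treatment restaging in patients in CR".

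**The concern.** A scan confined to known sites cannot show that there are no new ones. Take a patient with mediastinal disease at baseline whose nodes shrink by half while new retroperitoneal nodes appear. Under 5.3 this is PD. On a chest-only CT, which footnote C permits, it can be scored PR.

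Response rate is a primary objective (1.1.1), and each histology cohort is compared with a fixed 20% rate (Section 6). There is no concurrent control in which the same error would occur and cancel. Because the extent of the scan is discretionary, ascertainment can also differ between patients.

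**Working it through.** **1. Field imaged against field needed**

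| Outcome | What 5.3 needs outside known sites | What a limited CT shows there |
|---|---|---|
| PR | No new sites (explicit) | Nothing |
| PD | New lymph nodes alone suffice (explicit) | Nothing |
| CR | No detectable radiographic disease (implied) | Nothing |

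**2. Is the gap closed elsewhere?** Not by any provision I can find.
- Physical examination each cycle finds palpable disease, not deep nodes.
- PET after treatment is optional and confined to patients already in CR, so it never covers PR.
- Weekly LDH and blood counts, and the LDH condition for CR, are indirect and image nothing.
- The rule in 5.3 that a response must last at least 4 weeks off treatment does not ensure a full scan, because the follow-up CT carries the same footnote.
- No section requires full-field CT before a response is scored.

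**3. Direction.** Measurement of the known sites is unaffected by the narrower field. Unseen new disease can therefore turn PD into CR, PR or SD, never the reverse. PD read as CR or PR adds a false responder. PD read as SD leaves the response rate unchanged, because both are non-response.

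**4. The plan's own design, reproduced.** Inputs from Section 6: p0 = 0.20, p1 = 0.45, α = β = 0.10; stop if 3 or fewer of 14 respond; success if 8 or more of 25 respond.

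With X1 ~ Bin(14, p) and X2 ~ Bin(11, p):
- Early termination = P(X1 ≤ 3).
- Declared active = Σ over x = 4 to 14 of P(X1 = x) × P(X2 ≥ 8 − x).

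At p = 0.20:
- Early termination = 0.0440 + 0.1539 + 0.2501 + 0.2501 = 0.698, matching the stated 70%.
- Declared active = 0.1720×0.1611 (x = 4) + 0.0860×0.3826 (x = 5) + 0.0322×0.6779 (x = 6) + 0.0092×0.9141 (x = 7) + 0.0024 (x ≥ 8) = 0.0277 + 0.0329 + 0.0219 + 0.0084 + 0.0024 = 0.093.

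At p = 0.45, declared active = 0.903. The sample size and decision rules are therefore correct as stated.

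**5. Illustration of the consequence.** The documents do not say how often new disease arises outside the baseline regions, or how often scans would be narrowed. I therefore assume that false responses add d to a true rate of 0.20, and evaluate the same formulas at p = 0.20 + d. The last column is d/(0.20 + d).

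| d (points) | Apparent rate | Early termination | False-positive probability per arm | Share of apparent responders that are false |
|---|---|---|---|---|
| 0 | 20.0% | 0.698 | 0.093 | 0 |
| 0.5 | 20.5% | 0.681 | 0.105 | 2.4% |
| 1 | 21.0% | 0.663 | 0.117 | 4.8% |
| 2 | 22.0% | 0.628 | 0.143 | 9.1% |
| 5 | 25.0% | 0.521 | 0.239 | 20.0% |

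The slack between 0.093 and the planned 0.10 is used up at an apparent rate of about 20.3%.

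**The case against.** The footnote is permissive. The calendar row itself is full chest, abdomen and pelvis CT, so the full field is the default, and nothing shows how often it would be narrowed. A false response needs four things together: baseline disease confined to part of that field; a decision to narrow the scan; known disease that regresses enough to count as a response; and new disease confined to the unscanned part and not clinically apparent. Where baseline disease already spans all three regions, the footnote has no effect. Section 1.2.5.1 says MCL usually presents at advanced stage. That describes presentation rather than relapse, but it suggests a smaller effect in the MCL arm.

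All of this stands, and it limits the size of the effect. It does not remove the conflict between 3.4 and 5.3 or change its direction.

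A reader might infer that response will be overstated in this trial, or that the false-positive probability is 0.239. The documents support neither. The 5-point case supposes that one apparent responder in five is false, and nothing in the plan points to that. A reader might also infer that CR, PR and PD all name new sites; only PR and PD do.

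**Conclusion.** The conflict holds on the text: the permitted restaging field can be smaller than the field on which PR, PD and, by implication, CR depend. In patients whose baseline disease does not span chest, abdomen and pelvis, PD can be scored as PR or CR, and the primary response rate can be overstated but not understated.

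The amount is unknown and may be close to zero, more so in MCL if disease is widespread. The tabulated probabilities rest on a true rate of exactly 20%, an assumed inflation, and scoring from the limited scan alone. They show that the rule has little slack, not that the error rate has moved by any given amount. Applying one inflation to both arms is a simplification.

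Confidence is high for the conflict in wording and its direction, and low for any particular size. The change is worth making because it is cheap and protects the primary endpoint.

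**What to change.** 1. At restagings used for the response endpoint, require the same chest, abdomen and pelvis CT field as at baseline, plus any other site positive at baseline. At minimum, require this before CR, CRu or PR is declared or confirmed.
2. Confine footnote C to follow-up after the response endpoint is settled.
3. Reword the restaging lines in 3.2.1 and 3.2.2 to match.
4. For limited scans already done, flag them in the data and add a sensitivity analysis that counts responses resting only on such scans as non-response. Report it beside the main response rate for each histology.

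The edit is one footnote and one line in each of two sections, plus the analysis. The full CT is already the calendar entry. The cost to patients is a somewhat larger scan field and more radiation where disease is localized. New disease outside both the CT field and the baseline sites would still depend on clinical examination.

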3.5 OFF STUDY CRITERIA

- Voluntary withdrawal.
- Institution of non-protocol treatment.
- Non-compliance which affects safety or endpoints of the study.
- Physician’s determination that withdrawal is in the patient’s best interest.

3.6 POST TREATMENT EVALUATION

Follow-up to occur every 3-4 months until disease progression that requires institution of non-protocol treatment. Adverse event data that occurs during the follow-up period that is unrelated to study treatment will not be reported. Patients who are taken off-protocol will continue to be followed for survival.

4 SUPPORTIVE CARE

4.1 TUMOR LYSIS SYNDROME

See section 4.3 in Treatment Modification Section

4.2 ANTI-EMESIS

Patients may receive prophylactic anti-emetics with ondansetron or granisetron.

